### **6.3 Safety Secondary Endpoints**

The following observations are considered as endpoints evaluating the safety and will be assessed at 30 days. They are ordered according to medical importance in the indication acute myocardial infarction.

- Total fatal stroke
- Total disabling stroke
- Total non-disabling stroke
- Intracranial haemorrhage

- Ischaemic stroke
- Total stroke (all types)
- Major non-intracranial bleeds (total, with blood transfusion, without blood transfusion)
- blood transfusions
- Minor non-intracranial bleeds
- Total non-intracranial bleeds
- Serious resuscitated ventricular fibrillation
- Serious resuscitated ventricular fibrillation in association during with invasive procedures (occurring at any time during cath /and urgent/elective PCI)

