Dose and mode of administration	
Pre-hospital treatment:
 
In agreement with international guidelines, upfront antithrombin treatment, aspirin and a P2Y12 antagonist according to local standards and at the discretion of the investigator (e.g., unfractionated heparin/ enoxaparin or bivalirudin, clopidogrel or ticagrelor). Prasugrel is not recommended (cfr bleeding risk in elderly patients).
 
In-hospital treatment:
 
Maintenance dose of aspirin and a P2Y12 antagonist. Additional GP IIb/IIIa antagonists during PCI are at the investigator's discretion (eg for bail-out).

Criteria for efficacy	
Pharmaco-invasive strategy compared with primary PCI
 
Number of patients achieving $\geq 50\%$ ST-segment resolution before and after PCI in lead with maximal ST elevation at baseline; % rescue PCI; TIMI flow grades
 
Clinical events of interest i.e. death, shock, heart failure, recurrent MI, rescue PCI and aborted MI will be recorded and assessed as single or composite endpoints for evaluation.

Criteria for safety	
 - Total stroke, intracranial haemorrhage (ICH), ischaemic stroke, haemorrhagic conversion up to 30 days - Non-intracranial bleeds (total, major, minor, and blood transfusions) up to 30 days - Serious cardiac events (e.g. death, congestive heart failure, reinfarction, resuscitated ventricular fibrillation, repeat target vessel recanalization, stent thrombosis, total AV block etc) up to 30 days

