4.2.2 Restrictions

Enoxaparin and heparin

Patients who received enoxaparin should not be administered a different type of heparin prior to catheterisation (and vice versa) as this may result in excessive anticoagulation well above therapeutic levels.^{47,48} If heparin was initially used for PPCI patients, subsequent treatment should not be switched to enoxaparin prior to catheterisation.

Prior to catheterisation a dose of 0.3 mg/kg i.v. enoxaparin should be given to patients in Group PhI, unless the last subcutaneous dose of enoxaparin was given within the previous 8 hrs.

GP IIb/IIIa antagonists

GP IIb/IIIa antagonists should not be used in Group PhI except if required for bail-out situations in the catheter laboratory. The use of GP IIb/IIIa antagonists in PPCI arm is at the investigator's discretion in accordance with STEMI/PCI guidelines and local standards.

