5.2.2 Specific safety recording within 30 days

Specific safety events to be recorded in this trial will be:

- Clinically suspected stroke (total (fatal, disabling, non-disabling); ischaemic; intracranial haemorrhage)

Patients experiencing any new neurological deficit at any time after randomisation (up to day 30) are to be taken for immediate (within 24 hours) computed tomography scanning (CT) or

magnetic resonance imaging (MRI) to determine whether a stroke or intracranial haemorrhage (ICH) has occurred. CT is preferred, but MRI is also acceptable. In addition, all patients concerned should also be seen by a neurologist who may assist with the completion of the necessary documentation.

If, in case of a fatal stroke and no imaging was done, an autopsy should be performed whenever possible.

Detailed information on the stroke (date and time of onset, type, method of detection, outcome) will be collected in the eCRF.

If a stroke occurs after discharge (up to day 30) or after referral to another hospital, the investigator and/or study team ought to use their best efforts to obtain the required information from that hospital.

All strokes will be centrally adjudicated by the Stroke Review Panel (cf. section 8.10).

- Non-intracranial bleeds (total, major, minor, and blood transfusions):

Any reported bleeding, i.e. minor or major bleeds or any bleeding requiring blood transfusion, will be collected in the eCRF to assess the safety of the treatment. Serious bleeds will be reported as serious adverse events as described in section 5.2.1. All bleeds will be recorded in the eCRF. For bleed categories please refer to Appendices.

- Serious cardiac events:

Serious clinical events such as stent thrombosis, reinfarction, CHF, cardiogenic shock will be recorded in the eCRF. For all serious adverse events requiring expedited reporting according to the procedure described in section 5.2.1 a special eSAE form must be completed in addition and must be submitted for further distribution to the Coordinating Center within 24 hours of the investigator becoming aware of the event (see section 8.4.1).

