APPENDIX A: CLINICAL EVENTS TO BE RECORDED IN ECRF

Cardiac events within 30 days

- All-cause mortality
- Cardiac mortality
- Cardiogenic shock
- Congestive heart failure
- Recurrent myocardial infarction
- Stent thrombosis
- Rehospitalisation for cardiac reasons
- Rehospitalisation for non-cardiac reasons

Safety events with 30 days

Total stroke, intracranial haemorrhage, ischaemic stroke, haemorrhagic conversion within 30 days

- Procedure related major bleeds (within 48 hours)
- Non-intracranial bleeds (major, minor) and need for blood transfusions up to 30 days

Evaluations at 1 year

- All-cause mortality

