Data about any rehospitalisation for non-cardiac reasons occurring after discharge from initial hospitalisation until day 30 will be collected in the eCRF and have to be recorded on SAE reports in accordance with section 5.2.1. Only if rehospitalisation was scheduled, e.g. because of a routine or planned procedure, will it not be considered as a serious adverse event.

Statistical analysis of clinical events

The analysis will be described in detail in the statistical analysis plan. Clinical events of interest will be assessed as single or composite endpoints for evaluation. All statistical tests on clinical events are of exploratory nature based on descriptive statistics for formal statistical hypotheses generation. For comparison the same composite clinical event rates as in STREAM-1 will be analysed (see APPENDICES). The primary comparisons will be based on the differences between Group PhI and PPCI. Differences between groups and their 95% CI will be calculated. Should a statically significant difference appear in at least one clinical endpoint, i.e. the corresponding CI excludes 0 (no difference), and if there is also consistency for the other endpoints, then this will be considered evidence for a clinically meaningful difference between treatments which should be confirmed in a later study. Should no statistically significant difference be apparent, the CI will be examined to determine to what level a worse outcome can be excluded as has been done with the primary endpoint in STREAM-1.

A formal interim analysis will be performed after 50 % of the planned recruitment. The aim of this analysis is to evaluate the usefulness and feasibility of enlarging the study based on the results.

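### Stent thrombosis and 48-hour procedure-related major bleeds must be recorded under the protocol, but the SAP reports neither as such

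*SAP*

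**What the plan says.** The protocol synopsis, under its safety criteria, gives examples of serious cardiac events that include "repeat target vessel recanalization, stent thrombosis, total AV block etc) up to 30 days". Protocol 5.2.2 states that "Serious clinical events such as stent thrombosis, reinfarction, CHF, cardiogenic shock will be recorded in the eCRF". Appendix A, which lists events for the eCRF, gives "Stent thrombosis" its own line among the 30-day cardiac events. Among the safety events it has "Procedure related major bleeds (within 48 hours", on a separate line from non-intracranial bleeds up to 30 days. On how clinical events will be analysed, Appendix B says "The analysis will be described in detail in the statistical analysis plan", and Protocol 7.5 likewise defers to the SAP.

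SAP 6.3 introduces its safety list with "The following observations are considered as endpoints evaluating the safety and will be assessed at 30 days". The list covers stroke and its subtypes, major, minor and total non-intracranial bleeds, transfusions, and resuscitated ventricular fibrillation, including a subset tied to invasive procedures. Stent thrombosis and 48-hour procedural bleeds are absent.

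Antiplatelet rules differ by arm. Protocol 4.2.2 states "GP IIb/IIIa antagonists should not be used in Group PhI except if required for bail-out situations in the catheter laboratory", whereas "The use of GP IIb/IIIa antagonists in PPCI arm is at the" investigator's discretion. PhI patients receive clopidogrel (4.1.4.1). PPCI patients receive a P2Y12 antagonist chosen by local practice (4.1.4.2).

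**The concern.** The trial asks whether lysis, clopidogrel and later catheterisation are as effective and safe as primary PCI. The arms differ in antiplatelet rules and in the timing of catheterisation, so stent thrombosis and bleeding around the procedure are natural safety questions. Under the SAP as written, the planned output contains no between-arm figure for stent thrombosis, a safety criterion the protocol names. It also contains no count of procedural major bleeds, although the protocol requires both to be collected. If they are reported later, after the data have been seen, they will be post hoc.

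**Working it through.** No figure in the plan needs reproducing: N is about 600 (400 PhI, 200 PPCI), with no primary hypothesis or endpoint formulated (Protocol 7.5). The check is one of coverage, followed by a look at what precision the added rows would have.

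**Step 1. Coverage.**

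| Outcome | Protocol | SAP 6.1–6.6 and displayed tables | Nearest retained item |
|---|---|---|---|
| Stent thrombosis, 30 days | Synopsis safety criteria; 5.2.2; Appendix A | None | Reinfarction (6.2); rehospitalisation (6.2); serious abrupt vessel closure and serious recurrent ischaemia, in hospital (6.6) |
| Procedure-related major bleeds, 48 h | Appendix A | None | Major non-intracranial bleeds, 30 days (6.3) |
| Repeat target-vessel recanalisation | Synopsis list of examples only | None | PCI planned after the study PCI (6.6) |

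The SAP kept other items from the same synopsis list: resuscitated ventricular fibrillation (6.3) and AV block within serious major arrhythmias (6.6).

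**Step 2. Where a stent thrombosis would be counted.**
- As reinfarction, if Appendix B is met. More than 48 h after PCI, stent thrombosis is a supporting criterion, but a troponin rise or fall is also required. Within 48 h, the definition needs a troponin rise from a baseline that is normal, or raised and stable or falling. Early in a STEMI troponin may still be climbing, so some early cases may not qualify.
- In hospital, as serious abrupt vessel closure or serious recurrent ischaemia (Table 15.1).
- After discharge, as a rehospitalisation. SAP 8.6 treats only reinfarction and CHF as cardiac reasons and puts all others with stroke/ICH as non-cardiac. A stent-thrombosis readmission not coded as reinfarction is therefore tabulated as non-cardiac.

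No row identifies the event as stent thrombosis.

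**Step 3. Precision for stent thrombosis.** The documents give no rate, so 1% to 3% in both arms is assumed.
- Expected events: 400p and 200p, i.e. 4 and 2 at 1%, 12 and 6 at 3%.
- Half-width of the 95% CI for the risk difference: 1.96 × √[p(1−p)/400 + p(1−p)/200]. At 1%: 1.96 × √0.00007425 = 0.017. At 3%: 1.96 × √0.00021825 = 0.029.
- 95% CI around RR = 1: exp{±1.96 × √[(1−p)/(400p) + (1−p)/(200p)]}. At 1%: exp(±1.96 × √0.7425) = 0.18 to 5.41. At 3%: exp(±1.96 × √0.2425) = 0.38 to 2.63.
- Power for a doubling in PhI, two-sided 5%: Φ[(Δ − 1.96·SE₀)/SE₁], with SE₀ the pooled and SE₁ the unpooled standard error. 1% vs 2%: Φ[(0.010 − 1.96 × 0.01109)/0.00992] = 12%. 3% vs 6%: Φ[(0.030 − 1.96 × 0.01887)/0.01693] = 34%.

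**Step 4. Bleeds.** Protocol 7.5 gives STREAM-1 rates of 8.8% and 7% for major non-intracranial bleeding in patients aged 60 or over. Expected events are 400 × 0.088 = 35.2 and 200 × 0.07 = 14. The half-width on the 1.8-point difference is 1.96 × √(0.088 × 0.912/400 + 0.07 × 0.93/200) = 1.96 × √0.00052614 = 4.5 points. A 48-hour subset has fewer events still; the documents do not say what share it would be.

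**Step 5. The 48-hour window.** Appendix A does not say from when the 48 hours run. Scheduled PhI catheterisation is 6–24 h after tenecteplase (Protocol 6.2.2.1). A window starting at first catheterisation would then end 6 + 48 = 54 h to 24 + 48 = 72 h after lysis and would leave out the first 6–24 h. In PPCI it would start soon after arrival. The two windows cover different periods after randomisation, and patients without catheterisation have none.

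**The case against.** The best defence is that little is lost. A stent thrombosis with the required troponin change counts as reinfarction, which is part of the composite of primary interest. Procedural major bleeds are already in the 30-day total. The protocol's clinical events of interest (synopsis, 5.1.2) do not include either item, Appendix A lists events to record rather than endpoints, and the trial is hypothesis-generating. Steps 3 and 4 confirm that any comparison would be imprecise.

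Much of this stands. A reader might infer that a stent thrombosis short of reinfarction would appear in no table; the rows in Step 2 show otherwise. What is lost is the ability to identify it. A reader might also treat repeat target-vessel recanalisation as a third collected outcome left unanalysed. It appears only among examples in the synopsis and not in Appendix A, and the SAP History says that whether a planned later PCI took place is not recorded, so collection is not shown. Nor does the SAP History show a deliberate removal: it logs changes between SAP versions and mentions none of these items.

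The contrast between arms should not be overstated. Clopidogrel is a permitted PPCI agent, the synopsis gives bail-out as an example of GP IIb/IIIa use there too, and nothing in the documents ranks these outcomes as the most sensitive to the difference.

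The defence does not justify silence on stent thrombosis. It is named in the safety criteria, not only in a recording list. Low event numbers did not keep stroke subtypes out of SAP 6.3, and Protocol 7.5 promises events with 95% confidence limits.

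**Conclusion.** The point holds as a reporting gap that should be closed. Two outcomes that the protocol requires in the eCRF, one of them a named 30-day safety criterion, have no identifiable row in the SAP, and the readmission rule in SAP 8.6 can place some stent thromboses under non-cardiac reasons. The primary-interest analysis is not invalidated, and neither power nor type I error is at issue.

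At an assumed 1–3% rate, stent thrombosis would give 6 to 18 events in total and a risk difference known to about ±1.7 to ±2.9 points. That supports descriptive reporting with intervals, not a conclusion that the arms are alike. The number of 48-hour procedural bleeds cannot be derived from the documents. The verdict assumes that the eCRF holds what Protocol 5.2.2 and Appendix A require; the eCRF itself is not among the documents.

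**What to change.** - **Stent thrombosis (30 days):** add to SAP 6.3 and Table 12.1 as counts by arm, with the SAP 8.5.1 relative risk and risk difference and 95% CIs, labelled exploratory because events will be few. SAP 8.5.1 already has a rule for an arm with no events. Appendix B has no standalone definition, so state which one the eCRF entry used.
- **Procedure-related major bleeds (within 48 hours):** add as recorded in the eCRF, as a descriptive breakdown under 30-day major non-intracranial bleeds by arm, and state the starting point of the window. Keep the 30-day total as the between-arm comparison, because catheterisation timing differs by arm.
- **Repeat target-vessel recanalisation:** report it if it was captured; otherwise state that it was not.
- **Agent use:** no new table is needed. Tables 5.1 and 6.1 already give P2Y12 and GP IIb/IIIa use.

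The cost is a few lines of SAP text, one more exploratory comparison and one more descriptive row, using data that the protocol requires.

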#### **6.4 Combined Efficacy and safety Endpoints**

The following combined efficacy and safety endpoints will be assessed at day 30.

- All cause death and non-fatal stroke
- All cause death and shock and CHF and reinfarction and disabling stroke

#### **6.5 Other Endpoints**

##### **6.5.1 Within 30-days**

- Duration of index hospitalization

##### **6.5.2 Evaluations at 1 year**

- All-cause mortality
- Rehospitalization for cardiac reasons
- Rehospitalization for non-cardiac reasons

#### **6.6 Additional in-hospital events**

- Serious major arrhythmias (defined as AV block, atrial fibrillation, sustained ventricular tachycardia, ventricular fibrillation or asystole)
- Serious EMD
- Serious cardiac rupture
- Serious acute ventricle septum defect

- Serious pericarditis
- Serious tamponade
- Serious sustained hypotension
- Serious recurrent myocardial ischemia
- Serious abrupt vessel closure
- Serious coronary spasm
- Serious coronary arterial dissection
- Serious hypersensitivity
- Serious anaphylactoid reaction
- Serious thrombocytopenia
- Drop of hemoglobin > 5 g/L
- PCI planned (after study PCI)
- CABG planned (after study catheterization / study PCI)

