^c Renal function: A laboratory test of serum creatinine clearance (as per Cockcroft-Gault formula) should be done at the first occasion to rule out renal insufficiency or, if applicable, to adapt the dose of subcutaneous enoxaparin according to protocol in Group PhI patients with low creatinine clearance.

^d Cardiac biomarkers : The first available value (pre-hospital or upon arrival at hospital) should be recorded. Additional values should be taken 8-12 hours and 24 hours after randomisation. Cardiac biomarkers should also be taken in case of signs and symptoms suggestive of recurrent myocardial ischaemia or reinfarction until day 30.

^e Twelve-lead ECG in Group PhI: In the receiving hospital an ECG will be recorded 90 min after injection of tenecteplase or earlier, if clinically indicated, for assessment of ST resolution. If planned catheterization or rescue or

urgent PCI is done, ECGs will be taken immediately before the procedure and 30 min after the end of the procedure, respectively.

Twelve-lead ECG in Group PPCI: In the receiving hospital an ECG will be taken prior to the PCI procedure and 30 min after the end of the procedure.

In all patients, in addition to baseline and possible in-hospital ECGs, an ECG will be recorded before hospital discharge. Serial in-hospital ECGs should be taken in case of symptoms of recurrent ischaemia or reinfarction. ECGs will be centrally adjudicated.

^f Killip class will be determined prior to randomization (or, if this is not possible, immediately on hospital arrival).

^g Patients randomized to Group PhI will receive the trial medication in the ambulance/ER community hospital immediately after randomization. Patients randomized to PPCI will receive medication in the ambulance/ER community hospital and/or prior to PPCI according to the local hospital standards.

^h In Group PhI catheterization and PCI should be delayed for at least 6 hours, but no longer than 24 hours after randomization, if ST resolution is $\geq 50\%$ and no rescue or urgent PCI is indicated (for details refer to section 6.2.2.1); whereas in Group PPCI all patients are expected to receive catheterization and PCI according to local standards. Catheterization and PCI data will be recorded in the eCRF (cf. section 6.2.2.2).

ⁱ Serious clinical events will be recorded until and including day 30.

^j Visit at 30 days either at outpatient clinic or via phone.

^k Visit at 1 year either at outpatient clinic, via phone or from medical records.

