Troponin I/T (or CK, CK-MB) will be measured at baseline, i.e. pre-hospital or on arrival at ER of the community hospital, as well as 8-12 hrs and 24 hrs after randomisation. If symptoms suggest occurrence of recurrent myocardial ischaemia or reinfarction during in-hospital stay, marker levels should be determined to confirm the diagnosis. Individual values will not be recorded in the eCRF, for the qualifying myocardial infarction only peak values expressed as times exceeding upper limit of normal will be recorded (cf. also section 5.1.2).

- 12-lead ECG:

For ECG measurements please refer to section 5.1.2.

- TIMI flow grade:

TIMI flow grade of the infarct-related artery (IRA) will be assessed by standard angiographic measurement during routine catheterisation in Phi Group or, for the PPCI Group, before PCI (first contrast injection) and after PCI (last contrast injection) as measured by the local investigator.

- Killip class:

Killip class will be determined before randomisation to check for patient eligibility. In case the ambulance staff consists of paramedics only, the responsible PI (or sub-investigator) must make sure the staff is sufficiently trained to perform the Killip classification. In the exceptional case that the Killip classification cannot be done at randomisation, it will be done upon arrival at the hospital.

- Adverse events:

Expected adverse events (AEs) related to tenecteplase are listed in the current version of the Tenecteplase Investigator Brochure⁵⁰, filed in the Investigator Site File.

Adverse events will be recorded according to the following procedure until day 30 (cf. Figure 2):

All adverse events (serious and non-serious) need to be reported in the eCRF.

In addition an SAE form must be completed and submitted within 24 hours for any SERIOUS adverse event:

- related to study treatment (Tenecteplase, Clopidogrel, catheterisation/PCI)
- not related to study treatment AND not on the list of the STEMI related events

ADVERSE EVENT REPORTING

[figure not shown]

Figure 5: Adverse Event Reporting

During screening/baseline, the patient's condition is assessed; any relevant changes from

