6.2.3 End of trial and follow-up period

6.2.3.1 End of trial (day 30)

The end-of-trial visit will take place at day 30. Data may however be collected until and including day 37. If a visit at the outpatient clinic is not possible the patients may be contacted by phone. The following data will be collected:

- Data on any rehospitalisation occurring after hospital discharge up to (including) day 30
- Any occurrence of adverse events, and serious adverse events/serious clinical events since hospital discharge or (if the patient is still hospitalised) that have not yet been recorded

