Aborted myocardial infarction⁵⁴ will be assessed by means of ECG as ST-segment resolution relative to baseline value and cardiac marker enzymes as done previously in STREAM-1⁵⁵. Peak levels of troponin I/T (CK/CK-MB) will be collected at baseline, and 8-12 hrs and 24 hrs after randomisation. Quantification of aborted myocardial infarction will be defined as troponin values \leq 5 times the upper limit of normal (ULN) within 24 hours of randomisation (or CK/CK-MB levels \leq 2 times ULN). Only peak values of markers of necrosis (expressed as times exceeding the upper limit of normal) will be recorded in the eCRF; the complete set of measured values will however be kept in the source documents.

Rescue PCI post PPI therapy

If ST-segment resolution is $<50\%$ relative to the ST-segment elevation in the qualifying lead at baseline, irrespective of the presence or absence or clinical symptoms

Refractory ischaemia

Symptoms of ischaemia with ST-deviation or definite T-wave inversion persisting for at least 10 min despite medical management while in-hospital and not fulfilling the diagnosis of infarction.

Major arrhythmias

Sustained ventricular tachycardia (ventricular tachycardia lasting ≥ 30 seconds or requiring cardioversion or causing symptoms/hypotension), ventricular fibrillation, asystole, atrial fibrillation, 2nd and 3rd degree atrio-ventricular block.

Invasive procedures

Include CABG, PTCA, stent placement, intra-aortic balloon.

Other major cardiac events

Other major cardiac events include sustained hypotension, acute mitral regurgitation, acute ventricular septum defect, pericarditis, pulmonary embolism and tamponade.

Sustained hypotension

SBP < 90 mmHg for > 30 minutes

Rehospitalisation for cardiac reasons

If, after discharge, a patient is readmitted to the hospital until day 30 due to cardiac reasons, this information must be recorded in the eCRF. Any event requiring unscheduled readmission will be considered a serious adverse event (SAE) and recorded as described in section 5.2.1. Only if readmission was scheduled, e.g. because of a routine or planned procedure, will the event leading to rehospitalisation not be considered as a serious adverse event.

Rehospitalisation for non-cardiac reasons

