### **8.10 Additional in-hospital events**

The number of events and the percentage with respect to the number of subjects for that item will be reported in each treatment group. A Fisher's Exact test will be performed.

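### SAP 6.6 tabulates serious cardiac events such as AV block, rupture and tamponade in hospital only, although the protocol makes serious cardiac events a 30-day safety criterion and collects the data to day 30

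*SAP*

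**What the plan says.** **Protocol.** The synopsis, under criteria for safety, lists serious cardiac events. After death, heart failure and reinfarction, its examples continue with "resuscitated ventricular fibrillation, repeat target vessel recanalization, stent thrombosis, total AV block etc) up to 30 days". Footnote i of the Flow Chart states: "Serious clinical events will be recorded until and including day 30". Section 5.2.1 has adverse events recorded until day 30, and the day-30 visit (section 6.2.3.1) collects "Any occurrence of adverse events, and serious adverse events/serious clinical events since hospital discharge". Appendix B adds a definition that carries no time limit: "Other major cardiac events include sustained hypotension, acute mitral regurgitation, acute ventricular septum defect, pericarditis, pulmonary embolism and tamponade".

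**SAP.** Section 6.6, "Additional in-hospital events", has 17 items. Eleven are cardiac: major arrhythmias (a composite of AV block, atrial fibrillation, sustained ventricular tachycardia, ventricular fibrillation and asystole), electromechanical dissociation, cardiac rupture, septal defect, pericarditis, tamponade, sustained hypotension, recurrent ischaemia, abrupt vessel closure, coronary spasm and coronary dissection. The other six are hypersensitivity, anaphylactoid reaction, thrombocytopenia, a haemoglobin drop, planned PCI and planned CABG. Section 8.10 says of all of them: "The number of events and the percentage with respect to the number of subjects for that item will be reported in each treatment group". Fisher's exact test is then applied. Tables 15.1 and 15.2 follow that layout. Section 6.6 does not say when the in-hospital period starts or ends.

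**The concern.** The two documents give different windows for the same kind of event. The protocol promises a 30-day account of serious cardiac events and has sites collect the data for it. The SAP stops its table of these items at discharge and does not mention the difference. A tamponade or complete AV block in the weeks after discharge would be in the database but in no planned table under its own name.

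There is a second, conditional issue. Each patient is observed until his or her own discharge, and length of stay arises after randomisation. SAP 8.9.1 treats it as an outcome to be compared between arms. A crude proportion over patient-specific windows has no fixed time horizon. If one arm stayed longer, it would have more time to accumulate events.

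**Working it through.** **1. Is there another table to day 30?** The places in the SAP where such an event could appear are these.

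- Section 6.3 and Table 12.1 (30-day safety): strokes, bleeds, transfusions and serious resuscitated ventricular fibrillation. Among the arrhythmias, only the last is carried to 30 days.
- Section 6.2 and Table 11.1 (30-day efficacy): death, shock, heart failure, reinfarction and rehospitalisation. A post-discharge rupture or AV block enters here only if it leads to one of these.
- Section 8.6: for rehospitalisation, reinfarction and heart failure are the cardiac reasons, while stroke/ICH and all other reasons are non-cardiac. A readmission for tamponade or AV block would therefore be counted as non-cardiac.
- The SAP's list of tables has no general adverse-event or SAE table.

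The gap is therefore a by-type table after discharge. In addition, total AV block, which the protocol names, cannot be separated from the arrhythmia composite even in hospital.

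**2. How large could the gap and the distortion be?** The plan gives no figure to reproduce, and the documents give no stay by arm and no event timing. The following is an illustration under stated assumptions.

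Assume the same true 30-day risk in both arms, a share *f* of events by day 4, the rest spread evenly over days 4 to 30, and every patient in an arm staying *L* days (*L* at least 4).

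Captured share = *f* + (1 − *f*)(*L* − 4)/26. False relative risk = ratio of the two captured shares.

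Example, *f* = 0.5: at *L* = 5, 0.5 + 0.5 × 1/26 = 0.519, so 48% of events are missed. At *L* = 6, 0.5 + 0.5 × 2/26 = 0.538. The ratio is 0.538/0.519 = 1.04.

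| Share of events by day 4 | Missed at a 5-day stay | False RR, 6 vs 5 days | False RR, 7 vs 5 days |
|---|---|---|---|
| 4/30 (constant risk) | 83% | 1.20 | 1.40 |
| 50% | 48% | 1.04 | 1.07 |
| 80% | 19% | 1.01 | 1.02 |
| 90% | 10% | 1.004 | 1.009 |

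With equal stays the false relative risk is 1.00 in every row.

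**3. Chance of a false signal.** Take 400 PhI and 200 PPCI patients, a 10% true 30-day risk in both arms, the longer stay in PhI, and *f* from 4/30 to 0.8. The chance of a nominally significant excess in the longer-stay arm, against 2.5% nominal, is 2.7% to 4.2% for a one-day difference and 2.9% to 6.6% for two days. At a 2% risk it is 2.6% to 2.9% and 2.6% to 3.4%. These use a normal approximation, not Fisher's test, and are rough at such small counts.

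**4. After the change.** With a window from randomisation to day 30, the captured share is 100% in both arms and the false relative risk is 1.00, whatever the stays.

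**The case against.** **The in-hospital format was chosen.** The SAP history says the list was limited to serious in-hospital events to match STREAM-1 output. That explains the restriction to serious events and is a good reason to keep the in-hospital columns. It does not address the protocol's 30-day window.

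**The protocol is not uniform.** Appendix A, its list of 30-day cardiac events for the eCRF, omits AV block, rupture and tamponade. Outside total AV block, which is explicit, the 30-day reading rests on the open-ended wording of the synopsis together with general adverse-event recording. Appendix B confines refractory ischaemia to the hospital stay. Its own definition of major arrhythmias is a composite that includes AV block, so the SAP's grouping has a source. These points narrow the finding but leave the synopsis criterion unmet.

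**The trial is exploratory, and the main outcomes are safe.** Stroke, ICH, bleeding and the clinical composite all have fixed 30-day horizons, and the DSMB monitors safety during the trial. This stands, and it limits the importance of the point.

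**Stronger readings that the documents do not support.** A reader might infer that post-discharge events are never reported. They are collected to day 30, and those causing death or readmission are counted. A reader might infer that the arms are observed over unequal windows. No document gives stay by arm, and planning to compare stay does not show that it differs. The 4 days in the enoxaparin text of protocol section 4.1.4.1 are a treatment duration, which for patients of 75 years or more is expressly a maximum, so they cannot serve as an estimate of stay. Nor does back-transfer to a community hospital clearly shorten the window, since protocol section 5.3.1 counts that time in the stay. Finally, thrombocytopenia, hypersensitivity, anaphylactoid reaction, the haemoglobin drop and planned procedures are not serious cardiac events under the synopsis criterion.

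**Conclusion.** The point holds for the serious cardiac items in SAP 6.6. Their in-hospital window is shorter than the protocol's 30-day criterion, the departure is not explained, and no planned table shows these events by type after discharge. This follows from the text alone.

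The size of the omission is unknown. Under the assumed 5-day stay it ranges from about a tenth to more than four fifths of 30-day events, depending on how early they occur. Distortion of the between-arm comparison is only a possibility: it needs a difference in stay that the documents do not establish, and it is negligible if most events come in the first days. The change should be made because it closes a gap in the safety account at little cost. No planned main conclusion depends on it.

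**What to change.** In SAP 6.6, 8.10 and Table 15.1 (and 15.2 for the per-protocol set):

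- For the serious cardiac items, add columns for patients with at least one event from randomisation to day 30, taken from the adverse-event and SAE data already in the eCRF. Counting patients also gives Fisher's test a proper proportion.
- Make total AV block identifiable, as its own row or a sub-row of the arrhythmia composite, because the protocol names it.
- If the recurrent-ischaemia item is meant to follow the protocol's refractory-ischaemia definition, which applies only in hospital, say so and leave it in hospital.
- Keep the in-hospital columns for comparison with STREAM-1.
- Leave hypersensitivity, anaphylactoid reaction, thrombocytopenia, the haemoglobin drop and planned PCI or CABG in hospital if preferred.

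The minimum alternative is a sentence in 6.6 stating and justifying the departure from the protocol window. That would explain the gap without filling it.

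The cost is SAP wording, table shells and programming. The downside is one more set of columns, which has no STREAM-1 counterpart. No sample-size, power or alpha figure changes.
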